#### **1.3.2.1.1 Pharmacokinetic results**

Of the 62 patients who completed the study, 61 were included in the descriptive statistics of the ceftobiprole plasma concentrations, and 55 were included in the estimation of the plasma PK and exploratory PD parameters.

Overall, at the doses administered to patients aged < 12 years (15 mg/kg for patients aged < 6 years and 10 mg/kg for patients aged 6 years to < 12 years), the single-dose PK were generally within the range of what was previously observed in healthy adult subjects after a single ceftobiprole 500 mg dose. At the dose administered to patients aged 12 years to < 18 years (7 mg/kg, up to a maximum of 500 mg), the systemic exposure was substantially lower than that achieved in adults after a single ceftobiprole 500 mg dose.

#### **1.3.2.1.2 Safety results**

The safety assessments in this pediatric study showed that single-dose administration of ceftobiprole was safe and well tolerated by patients aged  $\geq$  3 months to < 18 years. No new or unexpected safety signals associated with ceftobiprole were detected.

#### **1.3.2.2 Study BPR-PIP-001**

The primary objective of study BPR-PIP-001 was to characterise the PK of ceftobiprole when administered as a 4-hour single-dose (7.5 mg/kg) infusion in neonates and infants aged  $\leq$  3 months. The secondary objective was to evaluate the safety and tolerability of ceftobiprole in this study population.

This was a multicenter, open-label, single-dose, Phase 1 study that planned to enroll 45 patients who had documented, or were presumed to be at risk of, bacterial infections, and who were already receiving systemic antibiotic therapy. This study enrolled 15 term neonates (gestational age  $\geq$  37 weeks).

#### **1.3.2.2.1 Pharmacokinetic results**

While all 15 patients enrolled in the study had measurable plasma concentrations, two patients had insufficient PK data for the non-compartmental analysis, and were therefore excluded from the PK analysis population.

Overall, exposure to the active moiety ceftobiprole was substantially higher than that for the prodrug ceftobiprole medocaril and the open-ring metabolite. The median maximum plasma concentration ( $C_{max}$ ) was highest for ceftobiprole (11.2  $\mu$ g/mL) compared to ceftobiprole medocaril (0.107  $\mu$ g/mL) and the open-ring metabolite (0.644  $\mu$ g/mL).

Ceftobiprole time to maximum concentration was reached at the end of infusion (i.e., at 4 hours) in all patients.

### 1.3.2.2.2 Safety results

The safety assessments in this pediatric study showed that single-dose administration of ceftobiprole at 7.5 mg/kg was safe and well tolerated by the neonate and infant population aged  $\leq$  3 months. No new or unexpected safety signals associated with ceftobiprole were detected.

### 1.3.2.3 Study BPR-PIP-002

The primary objective of study BPR-PIP-002 was to evaluate the safety profile of ceftobiprole in pediatric patients aged 3 months to  $<$  18 years with hospital-acquired bacterial pneumonia (HABP) or community-acquired bacterial pneumonia (CABP) requiring hospitalisation and IV antibiotic therapy.

The secondary objectives were to characterise the PK of ceftobiprole and to evaluate the efficacy of ceftobiprole versus IV standard-of-care cephalosporin treatment ( $\pm$  vancomycin) in this patient population.

This was a multicenter, randomized (2:1), Investigator-blind, active-controlled study that enrolled 138 patients (94 in the ceftobiprole group and 44 in the comparator group). Patients randomized to ceftobiprole received IV infusions every 8 hours (q8h) at age-adjusted doses and infusion durations as follows:

- 3 months to  $<$  2 years (12 patients, 20 mg/kg as 4-hour infusions)
- 2 years to  $<$  6 years (37 patients, 20 mg/kg as 2-hour infusions)
- 6 years to  $<$  12 years (27 patients, 15 mg/kg as 2-hour infusions)
- 12 years to  $<$  18 years (18 patients, 10 mg/kg as 2-hour infusions)

### 1.3.2.3.1 Pharmacokinetic results

The PK population comprised 33 patients who received at least one dose of ceftobiprole and had at least one ceftobiprole plasma concentration measurement obtained. Of these, plasma concentration-time data were available for 29 patients. Exposure to ceftobiprole was substantially higher than that for the prodrug ceftobiprole medocaril and the open-ring metabolite. Ceftobiprole peaked at the end of infusion (4 hours for patients  $<$  2 years and 2 hours for all other age groups).

In general, patients under 6 years of age (i.e., those who received ceftobiprole 20 mg/kg q8h) had higher ceftobiprole exposure and slightly longer half-life compared to patients aged 6 years or older. Mean  $C_{max}$  and area under the plasma concentration-time curve time zero to tau estimates were  $\sim$ 40% greater and half-life was  $\sim$ 16% longer in patients aged under 6 years compared to those 6 years or older ( $C_{max}$ : 33.3 versus 23.7  $\mu$ g/mL;  $AUC_{tau}$ : 108 versus 77.6 h. $\mu$ g/mL, respectively).

### 1.3.2.3.2 Safety results

The safety and tolerability of ceftobiprole in this study were consistent with the established safety profile for ceftobiprole in adults and with those of the cephalosporin class of

antibiotics. No new or unexpected safety signals associated with ceftobiprole were detected.

### 1.3.2.3.3 Efficacy results

Although the study was not powered to compare efficacy, this was the only pediatric study to-date that included efficacy objectives. The early clinical response rate at Day 4 was slightly higher in the ceftobiprole group than in the comparator group for both the intent-to-treat (ITT) and Clinically Evaluable (CE) populations, and at the test-of-cure (TOC) visit, the clinical cure rate was above 90% in both treatment groups, although lower in the ceftobiprole group than in the comparator group for both populations.

### 1.3.3 Benefit-risk assessment

Data from the clinical studies show that ceftobiprole can be safely administered to adult and pediatric (neonates to < 18 years of age) patients. Completed Phase 3 studies demonstrated the safety and efficacy of ceftobiprole in the adult population for various indications (HABP, CABP, and ABSSI), and in the pediatric population the safety and efficacy in patients with bacterial pneumonia were similar to those observed in adult patients. One Phase 3 study is currently ongoing to evaluate the safety and efficacy of ceftobiprole for the treatment of *S. aureus* bacteremia in adult patients.

The potential benefit to patients participating in this study is receiving antibiotic therapy for their infection, and the potential benefit of this study in general is the identification of a new addition to the available antibiotic therapy that is safe and effective for the treatment of LOS. It is possible that ceftobiprole will not prove to be a sufficiently effective treatment for LOS. This risk is mitigated by the optional addition of ampicillin and/or an aminoglycoside, by close monitoring of study patients, and by management with appropriate therapies as determined by the Investigator. The risk considerations for this study encompass the known and potential risks for ceftobiprole, as well as those risks associated with other treatments that may be administered (i.e., ampicillin and/or an aminoglycoside) as described in their respective prescribing information.

## 1.4 Study rationale

This study is part of a pediatric clinical development program to evaluate the use of ceftobiprole in patients < 18 years of age. Three completed pediatric studies, two Phase 1 and one Phase 3, are described in Section 1.3.2. Study BPR-PIP-001 assessed the PK and safety of single-dose ceftobiprole in term neonates and infants aged  $\leq$  3 months.

LOS is a major cause of morbidity and mortality among neonates and young infants. Pathogens responsible for LOS include CoNS, *S. aureus*, Enterobacterales, and *P. aeruginosa*. Ceftobiprole has a broad-spectrum bactericidal activity against most of these organisms, and was well tolerated in adult and pediatric clinical studies with a safety profile consistent with that of available cephalosporins. Therefore, ceftobiprole has the potential to become a therapeutic option in the treatment of LOS.

The purpose of this study is to assess the safety, tolerability, PK, and clinical effect of ceftobiprole, possibly combined with ampicillin and/or an aminoglycoside, in neonates and young infants up to 3 months of age with LOS.

#### 1.4.1 Summary of study design

This is a multicenter, open-label, single-arm, multiple-dose study of IV ceftobiprole in term and pre-term neonates and infants up to 3 months of age with LOS. Ceftobiprole may be combined with ampicillin and/or an aminoglycoside based on the Investigator's judgement, local standard of care, and/or isolated or presumed pathogens. At least eight patients, at least two term (gestational age  $\geq 37$  weeks) and at least six pre-term (gestational age  $\geq 24$  to 36 weeks), with post-natal age ranging from  $\geq 3$  days to  $\leq 3$  months will be enrolled.

The DSMB will review data on a regular basis to assess the safety of all patients enrolled in this study (see Section 3.4).

#### 1.4.2 Study design rationale

A single-arm study design is based on practical considerations, mainly the feasibility of recruitment and study evaluation of pre-term and term neonates and young infants with LOS. As the incidence of LOS is inversely proportional to gestational age (i.e., almost double in pre-term neonates  $\leq 32$  weeks as compared to term neonates [Dong 2015]), twice as many pre-term neonates than term neonates will be enrolled.

Immediate administration of empiric antibiotic therapy with broad-spectrum bactericidal activity is critical in neonates and young infants with LOS, in order to prevent morbidity and decrease mortality. The optional combination with ceftobiprole of ampicillin and/or an aminoglycoside allows for maximal coverage of Gram-positive and Gram-negative pathogens of LOS, particularly during initial empiric treatment, and in accordance with local pathogen epidemiology and local standard of care.

#### 1.4.3 Dose rationale

A three-compartment pediatric population PK model with linear elimination, clearance dependent on glomerular filtration, and other PK parameters scaled to body weight using a fitted coefficient consistent with allometric scaling principles, provided a robust fit to pooled data from studies CSI-1006, BPR-PIP-001, and BPR-PIP-002. Pre-defined model qualification procedures indicated that the final population PK model was expected to provide reliable estimates of ceftobiprole plasma exposure in the pediatric patients enrolled in these studies, and that the model was appropriate for the conduct of model-based simulations designed to identify appropriate ceftobiprole dosing regimens in pediatric patients (Rubino 2021a).

Model-based simulation analyses conducted using the final population PK model suggest that the following dosing regimens are predicted to result in consistent ceftobiprole exposure and adequate PK-PD target attainment for pathogens with a ceftobiprole MIC of 4 µg/mL ( $\geq 97.1\%$  of the pediatric population with a %FT>MIC above 40%):

- ceftobiprole 10 mg/kg infused over 2 hours and administered q12h in neonates and infants aged  $< 3$  months with a body weight  $< 4$  kg
- ceftobiprole 15 mg/kg infused over 2 hours and administered q12h in neonates and infants aged  $< 3$  months with a body weight  $\geq 4$  kg
- ceftobiprole 15 mg/kg infused over 2 hours and administered q8h in infants and children aged  $\geq 3$  months to  $< 12$  years with a body weight  $< 33$  kg
- ceftobiprole 10 mg/kg infused over 2 hours and administered q8h in adolescents aged  $\geq 12$  to  $< 18$  years with a body weight  $< 50$  kg
- ceftobiprole 500 mg infused over 2 hours and administered q8h in children with a body weight  $\geq 33$  kg and adolescents with a body weight  $\geq 50$  kg

Model-based simulations also indicated that the dose should be adjusted based on body weight or maximum allowable dose to avoid overly high exposures in the lightest infants ( $< 4$  kg), children  $\geq 33$  kg, and adolescents  $\geq 50$  kg.

Extrapolation of the model to pre-term neonates and young infants was deemed appropriate given the dependence of ceftobiprole PK on glomerular filtration rate and body weight, which are both well described in this population. Glomerular filtration rate was assigned using a standard equation that assumed normal renal function, adjusted for age and body surface area using fat-free mass ([Rhodin 2009](#)). Body weight and height were assigned using a set of polynomial longitudinal growth equations, which define body weight and height over time based on gender, gestational age, and post-natal age ([Troutman 2018](#)).

Model-based simulation analyses to assist in the ceftobiprole dose selection for the treatment of LOS in pre-term and term neonates and young infants assessed several dose regimens before identification of an optimal regimen ([Table 5](#)). The optimal dose regimen, with dose adjustment according to gestational and post-natal ages, was predicted to result in a consistent ceftobiprole exposure and adequate PK-PD target attainment similar to those in adults and older pediatric patients. In general, the median predicted AUC0-24 values fall within the mean  $\pm$  two standard deviations from the adult Phase 1 exposures from the multiple-ascending dose study. The 90% prediction intervals fall outside the range but remain acceptable. In contrast, ceftobiprole Cmax estimates were predicted to be lower than those observed in healthy adults, with the exception of the patients in the oldest gestational age group ( $\geq 37$  weeks), which are similar to adults.

## 2 OBJECTIVES OF THE STUDY

### 2.1 Primary objective

To characterise the safety profile of ceftobiprole in term and pre-term neonates and infants up to 3 months of age with LOS.

## 2.2 Secondary objectives

To assess in term and pre-term neonates and infants up to 3 months of age with LOS treated with ceftobiprole:

- PK of ceftobiprole
- Clinical response
- All-cause mortality
- Microbiological response

## 3 STUDY DESIGN

This is a multicenter, open-label, single-arm, multiple-dose study of IV ceftobiprole in term and pre-term neonates and infants up to 3 months of age with LOS. At least eight patients, at least two term (gestational age  $\geq 37$  weeks) and at least six pre-term (gestational age  $\geq 24$  to 36 weeks), with post-natal age ranging from  $\geq 3$  days to  $\leq 3$  months will be enrolled at approximately ten sites in Europe and USA, with additional sites and locations possible.

Study therapy consists of IV ceftobiprole medocaril for 3–10 days, which may be extended to 14 days if considered clinically necessary by the Investigator. Ceftobiprole may be combined with ampicillin and/or an aminoglycoside based on the Investigator's judgement, local standard of care, and/or isolated or presumed pathogens. If added, the treatment duration of ampicillin and/or an aminoglycoside is at the discretion of the Investigator.

Each patient is expected to complete the study in approximately 5–7 weeks, including screening, an estimated treatment duration of 3–10 days with possible extension up to 14 days, end-of-treatment (EOT) visit, TOC visit 7–14 days after last ceftobiprole dose, and a last follow-up (LFU) visit 28–35 days after last ceftobiprole dose.

[figure not shown]
Safety assessments will be done throughout the study. Specimens for microbiological assessment will be obtained as clinically indicated in accordance with local standard of care. Blood samples for PK analysis will be collected on Day 3. Efficacy outcomes will be assessed at the EOT, TOC, and LFU visits.

The DSMB will review data on a regular basis to assess the safety of all patients enrolled in this study (see Section 3.4).

### 3.1 Overview of study design and dosing regimen

An overview of the study design is provided in [Figure 1](#).

**Figure 1 Overview of study design**

EOT=end-of-treatment; IV=intravenous; LFU=last follow-up; TOC=test-of-cure.

Ceftobiprole medocaril powder for solution for infusion will be administered for 3–10 days (may be extended to 14 days if considered clinically necessary by the Investigator) as a 2-hour IV infusion according to the schedule in [Table 5](#).

Ceftobiprole medocaril may be combined with IV ampicillin and/or an aminoglycoside (gentamicin, tobramycin or amikacin) based on the Investigator's judgement, local standard of care, and/or isolated or presumed pathogens.

## 3.2 Endpoints

### 3.2.1 Primary endpoint

The primary endpoint is safety and tolerability in the Safety population, as assessed by AEs, SAEs, deaths, and discontinuations due to AEs during treatment with ceftobiprole and at the EOT, TOC, and LFU visits, as well as clinical laboratory tests, vital signs, and physical examination findings.

### 3.2.2 Secondary endpoints

#### *Pharmacokinetics*

- Plasma levels of ceftobiprole, ceftobiprole medocaril, and the open-ring metabolite in the PK population

#### *Efficacy*

- Clinical cure rate at the EOT and TOC visits (ITT and CE populations)
- All-cause mortality through Day 28 (ITT population)
- Microbiological eradication or presumed eradication rate at the EOT and TOC visits (mITT and ME populations)
- Improved signs and symptoms of LOS at the Day 3, EOT, and TOC visits (ITT and CE populations)

## 3.3 Treatment plan

### 3.3.1 Dose modifications

The intended dose of IV ceftobiprole may not be modified. As patients with moderate or severe renal impairment will be excluded, no need for dose adjustment is expected. Study drug may be discontinued at any time at the Investigator's discretion (see Section 4.4). If a patient's estimated glomerular filtration rate (using the Schwartz formula or other applicable formula) decreases to less than two-thirds of normal for the applicable age group, or urinary output decreases to  $< 0.5$  mL/kg/h (measured over at least 8 hours) during study drug treatment, ceftobiprole administration should be stopped and the patient should be switched to standard of care treatment. If continuation of ceftobiprole is considered necessary by the Investigator based on an individual medical benefit-risk assessment for a patient, then the implementation of real-time plasma level assessments of ceftobiprole is recommended.

If added, any dose modification for ampicillin and/or an aminoglycoside is at the discretion of the Investigator in accordance with local standard of care; aminoglycoside dose modification may be based on renal function or therapeutic drug monitoring.

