### 5.2.2 Active treatment visits

The following assessments and procedures will be performed during study treatment visits (Day 1 to Day 10 [or up to Day 14]; see [Table 3](#)):

- Study drug administration should be initiated as soon as possible after enrollment. Ceftobiprole medocaril will be reconstituted and diluted for IV administration and administered as described in the Pharmacy Manual and in Section [6.6](#). If applicable, ampicillin and/or an aminoglycoside will be prepared and administered according to the manufacturer's instructions and/or local standard of care. The dates and exact start and stop times of all ceftobiprole infusions, and if applicable, of all ampicillin and/or aminoglycoside infusions/injections must be recorded in the eCRF.
- Physical examination: complete or brief physical examinations focusing on changes from baseline during the active treatment period will be performed at the discretion of the Investigator as clinically indicated in accordance with local standard of care (see Section [5.5.2](#))
- Body weight (see Section [5.5.2](#)): body weight on Day 1, which will be used for Day 1 dose calculation, should be obtained within 12 hours prior to the first dose of study drug. From Day 2 until the last day of study treatment, the dose should be calculated based on the patient's first body weight of the day.
- Vital signs (including body temperature, respiratory rate, pulse rate, and systolic and diastolic blood pressures) and pulse oximetry must be recorded within 30 minutes before the first study drug administration, and then three times daily during the active treatment period. If continuously monitored, the highest body temperature, respiratory rate, and pulse rate, and the lowest systolic and diastolic blood pressures and oxygen saturation obtained during an 8-hour period, will be recorded (see Section [5.5.3](#)).
- Signs and symptoms of LOS (see Section [5.6.4](#))
- Local laboratory tests will be performed only if clinically indicated based on the Investigator's judgement in accordance with local standard of care (see Section [5.5.4](#)).
- If clinically indicated, measurement of urine output (over at least an 8-hour period). Use of a urinary catheter is based on the Investigator's judgement in accordance with local standard of care. Urinary catheters are not required for the purposes of this study.

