**Table 4 Local laboratory parameters**

Mandatory at Screening and the EOT visit; optional at active treatment visits and the TOC visit:		
Haematology	Blood chemistry	Urine analysis (dipstick)
Haematocrit	ALT	Blood
Red blood cell count	AST	Glucose
White blood cell count	Bilirubin (total)	Ketones
Absolute and immature neutrophils	Creatinine	Leukocytes
Platelets	Sodium	Nitrite
	Potassium	pH
	Bicarbonate	Protein

Optional at Screening and active treatment visits:	Blood chemistry
	Anion gap
	C-reactive protein
	Procalcitonin
	IL-6

EOT=end-of-treatment; ALT=alanine aminotransferase; AST=aspartate aminotransferase; TOC= test-of-cure.

Note: Optional blood tests may be performed at the discretion of the Investigator in accordance with local standard of care, taking into consideration the maximum allowable blood draw volumes.

See the Laboratory Manual for blood volumes to be drawn from each patient for the local laboratory tests and for PK sampling. The combined volume of blood samples taken for study purposes or as part of standard of care must not exceed the limit specified in the Laboratory Manual. Any deviations from this must be clinically justified.

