## 7 SAFETY

The role of the DSMB in ensuring the protection of patients' safety is described in Section 3.4.

Stopping criteria for individual patients are described in Section 4.4.

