## 13 APPENDICES

### Appendix 1 Renal function

For assessment of renal function, serum creatinine is typically used after the first week of life in term neonates and after 4 weeks in pre-term neonates. Before then, intra-individual changes (related to post-menstrual age) in serum creatinine are used as a guide to renal function.

In addition, the following references should be considered:

- Schwartz and colleagues ([Schwartz 2009](#)) published the following modified formula (based on serum creatinine levels determined with the enzymatic method):  

$$\text{Estimated glomerular filtration rate (eGFR; mL/min/1.73 m}^2) = 0.413 \cdot \text{length (cm)} / \text{creatinine (mg/dL)}$$
- Abitbol and colleagues ([Abitbol 2014](#)) reported serum creatinine levels of  $0.68 \pm 0.14 \text{ mg/dL}$  during post-natal days 3–7 in 60 pre-term neonates ( $34 \pm 3$  weeks). The same report presented a graph of eGFRs calculated with the modified Schwartz formula, in which the values of all age groups were  $> 20 \text{ mL/min/1.73 m}^2$ . Of note, the creatinine-based equation underestimated the GFR compared to the CysC-based equations, especially in pre-term neonates.
- Two graphs presented at an EMA Workshop on regulatory and scientific issues related to the investigation of medicinal products intended for neonate use ([Van den Anker 2006](#)) indicated that serum creatinine levels in neonates with a body weight  $> 1000 \text{ g}$ , or a gestational age  $> 27$  weeks, fell from a maximum of about  $110 \text{ } \mu\text{mol/L}$  on day 1 to about  $50 \text{ } \mu\text{mol/L}$  within 3 to 4 weeks.

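### The renal stopping rule in Section 3.3.1 has no mandatory on-treatment measurement behind it, and the Day 3 PK samples have no required same-day creatinine

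*Protocol*

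**What the plan says.** **The rule.** Protocol Section 3.3.1 has two renal criteria. One is met when eGFR "decreases to less than two-thirds of normal for the applicable age group". The other is met when urine output falls below 0.5 "mL/kg/h (measured over at least 8 hours) during study drug treatment". If either is met, "ceftobiprole administration should be stopped and the patient should be switched to standard of care treatment". The same paragraph lets the investigator continue on an individual benefit-risk assessment. No other stopping reason in the protocol carries a numeric threshold.

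**The measurements.** Table 4 lists creatinine in a block headed "Mandatory at Screening and the EOT visit; optional at active treatment visits and the TOC visit". Table 3 footnote 9 agrees. For the treatment period, Section 5.2.2 states: "Local laboratory tests will be performed only if clinically indicated based on the" investigator's judgement. Urine output is also conditional on clinical indication (Table 3 footnote 11). EOT is on the day of the last dose or within 24 hours of it. Screening results up to 48 hours before the first dose are accepted (Section 5.2.1). Footnote 19 adds nephrotoxicity monitoring for infants who also receive an aminoglycoside, following the local label and local practice.

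**How renal function is to be read.** Serum creatinine is typically used after the first week of life in term infants and after four weeks in pre-term infants. Appendix 1 continues: "Before then, intra-individual changes (related to post-menstrual age) in serum creatinine are used as a guide to renal function".

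**PK.** Samples are taken on Day 3 only (Section 5.7). Section 1.4.3 describes a population model with "clearance dependent on glomerular filtration".

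**The pointer.** Section 7 states: "Stopping criteria for individual patients are described in Section 4.4". Section 4.4 lists reasons such as an adverse event or an abnormal laboratory value, but not the renal rule.

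**The concern.** The rule applies during treatment, but the schedule guarantees its inputs only at the two ends of treatment. An infant whose renal function declines without prompting a test could complete the course before any result exists that could meet the criterion.

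The protocol gives its own reasons to care. Renal failure is an adverse event of special interest. The kidney was a toxicity target in rats. Elimination is mainly by glomerular filtration. Urine output of 0.5–1 mL/kg/h, just above the stopping level, is one of the qualifying clinical signs. At least six of the eight planned patients are pre-term, the group for which Appendix 1 relies longest on changes between serial creatinines.

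There are two analytical consequences:

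- Laboratory results are part of the primary safety endpoint, and Protocol Section 8.4.1.1 summarises the worst post-baseline value. For an infant with no clinical trigger, that may be the single EOT value.
- The Day 3 concentrations will inform how far the model extends to pre-term infants. That extension assigned GFR assuming normal renal function (Section 1.4.3). No renal value is required at the time of those samples.

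**Working it through.** **1. The plan's own renal figure.** Appendix 1 tabulates eGFR thresholds, offered for Exclusion criterion 7, from eGFR = 0.413 × length (cm) / creatinine (mg/dL), with creatinine 1.32, 1.10 and 0.88. Two checks:

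- 0.413 × 33 / 1.32 = 10.3
- 0.413 × 60 / 0.88 = 28.2

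All 84 cells reproduce. Length is measured only at Screening (Section 5.5.2), so creatinine is the only input to this formula that can change during treatment.

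**2. Mandatory renal measurements between baseline and EOT.** From Table 3 footnotes 9 and 11, Table 4 and Section 5.2.2, there are none for creatinine and none for urine output. Section 5.6.5 includes low urine output as a daily sepsis sign, but only in catheterised infants (catheters are not required) and only in the 0.5–1 mL/kg/h band, above the stopping level.

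**3. Infusions and time before the next mandatory creatinine.** Let d be the course in days and τ the dosing interval in hours. Assumptions: doses at exact intervals, 2-hour infusions, baseline creatinine 48 h before the first dose, and EOT chemistry 24 h after the end of the last infusion.

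- Infusions = 24d / τ
- Interval between mandatory creatinines = (48 + 24d − τ + 2 + 24) / 24 days

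| Course | Infusions, q12h / q8h | Longest interval (days), q12h / q8h |
|---|---|---|
| 3 days | 6 / 9 | 134/24 = 5.6 / 138/24 = 5.8 |
| 10 days | 20 / 30 | 302/24 = 12.6 / 306/24 = 12.8 |
| 14 days | 28 / 42 | 398/24 = 16.6 / 402/24 = 16.8 |

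The q8h figures apply to only one cell of the dosing table (gestational age 37 weeks or more, post-natal age 60–90 days). Pre-term infants fall under q12h.

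**4. Renal value nearest the PK samples.** Day 3 pre-dose is 48 h after the first dose.

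- Looking back, the last mandatory creatinine was taken 0–48 h before the first dose, so it is 48–96 h old (up to 104 h at the 8-hour sample).
- Looking forward, the next comes at most 24d − τ + 26 − 48 hours later: 38–42 h in a 3-day course, 206–210 h (8.6–8.8 days) in a 10-day course and 302–306 h (12.6–12.8 days) in a 14-day course.

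**5. Normal drift in creatinine over that gap.** Appendix 1 reports a fall from about 110 to about 50 µmol/L within 3–4 weeks, in neonates above 1000 g or above 27 weeks' gestation. If the fall is linear (an assumption), the slope is 60/28 = 2.14 to 60/21 = 2.86 µmol/L per day. The SAP defines no Day 0 (Section 4.3.3), so Day −2 to Day 3 is 4 days. Expected drift is 4 × 2.14 = 8.6 to 4 × 2.86 = 11.4 µmol/L.

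**The case against.** The strongest reply is that the protocol does allow renal testing on treatment and leaves the timing to clinicians. Table 3 marks chemistry and urine output in the treatment period on indication. Section 5.5 permits more frequent assessments, and Section 5.5.4 requires unexplained abnormal results to be repeated. Adverse events are followed continuously, vital signs are taken three times daily and weight daily. The note to Table 4 ties optional tests to blood-volume limits, a real constraint in this population. All of this stands. A reader might infer that renal function goes unmonitored, or that renal failure could be found only at EOT. The documents do not support either: testing is discretionary, not absent.

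A reader might also infer that high Day 3 concentrations could not be attributed to dose or to renal function. That is too strong. Screening and EOT creatinine, screening length and daily weight are collected, the population PK analysis is reported separately and its covariates are not described here, and in a 3-day course the EOT chemistry can fall on or near Day 3. What remains is that no matching test is required.

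Nor does the drift calculation make the screening value a poor covariate for every infant. It applies to the neonates Appendix 1 describes, in the first 3–4 weeks. Appendix 1 also refers to a stable level of about 0.5 mg/dL during the first two years, so older infants may show little drift.

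The toxicology should be kept in proportion. Rat kidney toxicity was seen at doses of 250 mg/kg and above, marmoset kidney findings were reversible without microscopic lesions, and the stated paediatric safety margin is 2 to 6.

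None of this supplies a required on-treatment input for the rule.

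**Conclusion.** The point holds. Section 3.3.1 is conditioned on on-treatment eGFR and urine output, and the schedule mandates neither between baseline and EOT. Where nothing prompts a test, up to 20 or 30 infusions in a 10-day course, or 28 or 42 in a 14-day course, can be given before the first result that could meet the rule. Mandatory creatinines can then be as much as 16.6–16.8 days apart. These are upper limits under the schedule's widest windows and exact dosing. They do not predict what sites will do. Infants on an aminoglycoside have additional monitoring, and the rule itself is a recommendation with an exception.

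The PK gap is secondary: the last mandatory creatinine can be 48–96 h old at the Day 3 pre-dose sample and, except in the shortest courses, no mandatory value lies close to the samples. The 8.6–11.4 µmol/L drift rests on the linear assumption and the subgroup stated above. The Section 7 cross-reference is incomplete on its face. The sponsor should correct these points, but they do not undermine the study as a whole.

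**What to change.** 1. Reconcile Section 3.3.1 with Table 3 (footnotes 9 and 11), Table 4 and Section 5.2.2, so that the inputs of the rule the protocol already states are collected during treatment. The threshold, the action, and any timing beyond Day 3 are for the sponsor to decide.
2. At minimum, record a local serum creatinine at the Day 3 pre-dose PK draw and make it available as a renal covariate in the PK dataset. This gives the rule one on-treatment value and the PK data a same-day renal value. It does not address the urine-output criterion, nor the remaining days of a longer course (up to 12.6–12.8 days to EOT in a 14-day course).
3. Add the renal criterion to Section 4.4, or have Section 7 also refer to Section 3.3.1.

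The cost is a protocol amendment and one eCRF field. If creatinine is taken from the existing Day 3 draw, no further venepuncture is needed. The extra blood is assumed to be a few tenths of a mL. It must be checked against the Laboratory Manual limit, which is not among the documents reviewed and which also counts blood taken for routine care.
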